### 7.2.3 INTERVENTION AND FOLLOW-UP

*Intervention and Follow-up Assessments.* All study participants will complete study related assessments/measures at mid-intervention (week 4, +/- 7 days), post-intervention (week 8, +/- 7 days), and at the 6-week (+/- 7 days) and 12-week (+/- 7 days) follow-ups. It is expected that all assessments will be delivered via REDCap Survey. For in person patients, a tablet will be available for participants to use at the UCCC if they are not able to access internet otherwise. For all virtual participants, surveys must be completed via the REDCap link. If participants do not have a valid email address then surveys may be completed by paper and pencil or over the phone with research staff. REDCap is a secure web application designed to support data capture for research studies, provider user-friendly web-based case report forms, real-time data entry validation, audit trails and a de-identified data export mechanism to common statistical packages. Participants will be compensated with \$10.00 gift cards for completing six and 12-week follow-up assessments. See section 7.2.7 for full quantitative assessment schedule.

---

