## 4 STUDY DESIGN AND ENDPOINTS

### 4.1 DESCRIPTION OF THE STUDY DESIGN

This study is a single site (University of Colorado Cancer Center), randomized control trial. It will investigate the implementation (i.e., feasibility, acceptability, and fidelity) and preliminary clinical efficacy of an ACT intervention plus TAU for chronic pain in cancer survivors compared to TAU alone. Following consent, participants will provide baseline data including demographic and clinical characteristics. Participants will be randomized to ACT plus TAU or TAU alone. Due to study design, it is not possible to blind either participants or investigators to study condition. Participants will complete assessments at baseline, 4-week intervention midpoint, 8-week intervention completion, 6-week follow-up, and 12-week follow-up.

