#### 4.2.2 SECONDARY ENDPOINTS

Changes in physical and emotional functioning in the intervention group will be compared to the control group. The primary outcomes are physical and emotional functioning as measured by the

SF-36. We hypothesize that improvements in physical and emotional functioning will occur over time in both groups, but will be greater for the intervention group at completion of the program and at six and 12-week follow-ups as compared to the control group. The SF-36 has been used in previous studies evaluating ACT and chronic pain [14, 15]. Furthermore, the use of physical and emotional functioning as primary endpoints directly aligns with the theoretical basis of acceptance-based therapies [15].

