## **6 STUDY THERAPY**

### **6.1 STUDY THERAPY AND CONTROL DESCRIPTION**

#### **Intervention Groups**

*Treatment as usual.* Treatment as usual will include ongoing provision of usual treatment options for pain management. This includes continued medication management for cancer related chronic pain by prescribing providers (e.g., oncologist, primary care provider), and access to supportive oncology services (e.g., social work). It may also include other behavioral pain management such as physical therapy, acupuncture, or massage. Psychotherapy (e.g., Cognitive Behavioral Therapy) is often used as TAU in chronic pain. All participants may pursue this treatment modality, as it is part of standard care; however, for participants randomized to the intervention condition, their specified psychotherapy will be the ACT group protocol. Data regarding participation in these services will be collected as stated above in section 5.3.

*ACT Intervention.* Intervention group participants will attend eight weekly, 90-minute, in person, group-based ACT sessions. Groups may occur in person or remotely (i.e., audio/visual teleconferencing). Groups will be initiated with no more than 10 participants and no fewer than 4 participants. If a new group is scheduled with 4-10 participants and enough patients are “no-shows” that cause the group number to fall below 4, the group will continue as is and this will not be considered a deviation. Sessions will be adapted from an efficacious ACT chronic pain treatment manual [14, 15]. Sessions will include key theoretical ACT constructs and strategies as they relate to chronic pain. A licensed clinical psychologist or licensed clinical social worker trained in ACT will facilitate all sessions. Participants in the ACT intervention group will also continue to receive medication management and other behavioral management interventions as described above in “treatment as usual”. Data regarding participation in these services will be collected as stated below in section 7.1.

See Table 2 for more detail.

Table 2. ACT Intervention Constructs/Targets

ACT Session	Topic/Targeted Component	Aims/Application to Chronic Pain

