Session 6 – Action-Getting Your Feet Moving	

• Treatment Review

• Committed Action

• Mindfulness

	

• Review of treatment progress and any areas of ongoing concern

• Planning for action

• Fostering willingness around potential internal barriers

• Continued mindfulness practice

Session 7 – Commitment	

• Willingness

• Committed Action

• Mindfulness

	

• Extended discussion of willingness

• Fostering commitment to actions and values even in the face of barriers

• Continued mindfulness practice

Session 8 – Lifelong Maintenance	

• Maintenance

	

• Fostering commitment

• Relapse prevention and setbacks

• Saying goodbye to group

---

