#### **6.1.1 DURATION OF THERAPY**

For the ACT intervention group, an 8-week therapy protocol will be used.

---

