### 7.2.6 UNSCHEDULED VISIT

ACT intervention participants who are unable to attend a group session will be offered an individual session in order to review material with the group provider. This includes “make-up” sessions, which may occur due to planned or unplanned events (e.g., vacation or illness). “Make-up” sessions must occur (any time) prior to next scheduled session. These sessions will be scheduled based on the availability of both the participant and the provider. The make-up session may occur either in-person or remotely.

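### The Week 8 post-intervention window opens 7 days early and is not tied to session 8, so an in-window ACT survey can precede the end of the program

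*Combined protocol and SAP*

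**What the plan says.** - **Window.** Section 7.2.3 times the assessment in both arms as "post-intervention (week 8, +/- 7 days". Footnote 5 of the schedule of events (7.2.7) applies the same symmetric window to the SF-36, PROMIS, CPAQ and CAAQ.
- **Program length.** Section 6.1 states: "Intervention group participants will attend eight weekly, 90-minute, in person, group-based ACT sessions". Section 6.1.1 adds: "For the ACT intervention group, an 8-week therapy protocol will be used". The schedule in 7.2.7 places session 7 in Wk 7 and session 8 in Wk 8. Table 2 gives session 8 content of its own, including "Relapse prevention and setbacks".
- **What the time point stands for.** Section 4.1 lists it as "8-week intervention completion". Section 4.2.2 hypothesises improvement "greater for the intervention group at completion of the program", and again at the two follow-ups. Aims 2 and 3 in 2.2 name the same three time points.
- **Anchor.** Section 7.2.2 counts the TAU Week 4 assessment from baseline. It gives no starting point for the ACT Week 8 assessment, and it allows baseline to fall up to two weeks before the intervention begins.
- **Make-up sessions.** Under 7.2.6, make-up "sessions must occur (any time) prior to next scheduled session". Session 8 has no next session.
- **Contrast.** The qualitative interview is explicitly held to Week 9 or later (7.2.4, and footnote 6 in 7.2.7). The quantitative outcomes have no comparable rule.

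**The concern.** The assessment is named for the end of the program, but its window is drawn symmetrically around the week in which the program ends. A survey on the early side of that window is fully compliant, yet the participant may still be in treatment. Only ACT has sessions that can be outstanding. Early surveys would therefore tend to pull the between-arm difference towards zero, whereas in TAU they only change the time since baseline.

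At stake is the interpretation of one contrast, SF-36 physical and emotional functioning at the end of the program. It is also the time point closest to the post-treatment effect of d = 0.61 on which 10.4 bases the sample size.

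**Working it through.** The plan states no figure on this point, so there is none to reproduce. The check is calendar arithmetic.

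**Inputs.** Eight sessions one week apart (6.1, 7.2.7). Window half-width 7 days (7.2.3, footnote 5). Baseline 0 to 14 days before session 1 (7.2.2). The ACT Week 8 anchor is not stated, so each plausible one is tried.

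**Sessions.** With session 1 on day 0, session k falls on day 7(k − 1). Session 6 is on day 35, session 7 on day 42 and session 8 on day 49.

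**Window.** It opens on the Week 8 target day minus 7.

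| Week 8 counted as | Target day | Opens | Outstanding at opening |
|---|---|---|---|
| Date of session 8 | 49 | 42 | Session 8; also session 7 if completed before that day's session |
| Last day of the eighth program week | 55 | 48 | Session 8 |
| 8 weeks after session 1 | 56 | 49 | Session 8 only if completed earlier that same day |
| 8 weeks after baseline, same day as session 1 | 56 | 49 | As the row above |
| 8 weeks after baseline, 7 days before session 1 | 49 | 42 | As the first row |
| 8 weeks after baseline, 14 days before session 1 | 42 | 35 | Sessions 7 and 8; also session 6 if completed before that day's session |

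**When more than one session is outstanding.** With baseline b days before session 1, a baseline-anchored window opens on day 49 − b. Session 7 (day 42) lies after the opening day when 49 − b < 42, that is, b of 8 to 14 days. Otherwise a second outstanding session requires the form to be completed before session 7 on the opening day itself.

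**Follow-ups.** Assume they are counted from the Week 8 target. Even with the earliest target in the table (day 42), the 6-week window opens on day 42 + 42 − 7 = 77, which is 28 days after session 8. Both follow-ups fall after all scheduled sessions.

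**Size.** If a share p of ACT participants answer early and each lacks a fraction f of the benefit, the expected effect is d(1 − p·f). The documents give neither p nor f. If benefit were equal per session (an assumption), one missing session gives f = 1/8, and as p runs from 0 to 1 the effect runs from 0.61 to 0.61 × 0.875 = 0.53. The two-session edge case with p = 1 gives 0.61 × 0.75 = 0.46. With 46 per arm and two-sided alpha 0.05, a simple two-group comparison has power Φ(d√(46/2) − 1.96):

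- d = 0.61: 0.83
- d = 0.53: 0.73
- d = 0.46: 0.59

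The last two are worst-case bounds, with every ACT participant answering at the earliest date. They are not forecasts.

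**Time since baseline.** An ACT survey on the session 8 date falls 49 + b days after baseline, so 49 to 63 days. If the TAU Week 4 rule carries over to Week 8 (an assumption), the TAU target is 56 days. Any change to the ACT window therefore needs a stated TAU anchor.

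**The case against.** The strongest reply is that the time point is named by its event. An assessment called post-intervention would ordinarily be sent after the last session, with 7 days as tolerance around it. On that view the gap is a missing enforcement rule and not a plan to measure early. This stands in part: the documents do not say when surveys are released, so one cannot claim that early surveys will occur, only that they are allowed. The label does not close the gap, because the explicit window accepts an earlier survey without a deviation.

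The result also depends on the anchor. If Week 8 means eight weeks after session 1, the window opens on the day of session 8 and almost nothing is lost. That is correct, and it is a reason to state the anchor.

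Two stronger readings are tempting, and the documents support neither:

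- **That the end-of-program effect is cut by 12.5% to 25%.** This needs equal benefit from each session and applies only to early responders. Table 2 describes session 8 as maintenance and closing, while most core skills are introduced earlier, so one-eighth of the benefit cannot be assigned to it.
- **That PROMIS's seven-day recall makes matters materially worse.** PROMIS is exploratory. A seven-day recall answered on the day of session 8 also looks back almost entirely over days before that session.

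Finally, efficacy is secondary and preliminary, Week 8 is one of five time points in the repeated measures analysis (10.3.3), and the bias runs towards no effect. All of this limits the importance of the point.

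**Conclusion.** The point holds, with modest reach. The window as written admits ACT outcome data recorded before the final session under every anchor examined, although under the mildest ones only on the day of session 8 itself. One outstanding session follows from the natural reading; two or more need the particular conditions shown above.

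The likely consequence is some dilution of the end-of-program contrast in SF-36 functioning and in the exploratory outcomes. Its size cannot be derived from the documents, and the figures of 0.53 and 0.46 should not be quoted as expected effects. The primary implementation outcomes and the 6- and 12-week contrasts are not affected. This is still more than a missing detail, because a stated rule accepts mistimed data in one arm only, and correcting it is cheap.

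**What to change.** In 7.2.3 and footnote 5 of 7.2.7:

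1. State what Week 8 is counted from in each arm.
2. Open the ACT post-intervention window no earlier than the group's scheduled session 8 date, for example 0 to +7 or 0 to +14 days, and release the REDCap survey after that session.
3. Give TAU a window of the same length, anchored so that time since baseline is comparable between arms.
4. Time the ACT survey by the group's scheduled session 8 date and not by individual attendance. Holding a survey back until a person's make-up session would tie measurement timing to behaviour after randomisation in ACT only.

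The sponsor should also reconcile the make-up rule in 7.2.6, which has no end point for session 8, with the assessment window. The other windows can stay as they are.

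The cost is a few lines of protocol text and a changed survey release date. The early side is lost, so a few surveys may fall out of window unless the late side is extended. An extension to +14 days moves the latest post-intervention survey closer to the 6-week follow-up. If that follow-up is counted from the session 8 date, the gap to its opening would be 42 − 7 − 14 = 21 days, against 42 − 7 − 7 = 28 days with a +7 limit.

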### 7.2.4 FINAL STUDY VISIT

*Qualitative interview appointment.* Participants randomized to the intervention group may also be asked to participate in qualitative interviews regarding the acceptability of the intervention content and delivery following all quantitative assessment follow-up visits (any time during Week 9 through the 12-Week follow-up). Their invitation for participation will be determined by saturation of the data as explicated in the analysis portion of this document. Specifically, these data will be gathered through one-on-one, standardized open-ended interviews [22]. Interviews will be conducted using a semi-structured interview protocol [23], given either in person or over the telephone. The interview will be recorded, so that it can be transcribed and analyzed appropriately. Interviews will last approximately 30-45 minutes. Participants will be compensated with \$15.00 gift cards for completing this interview.

---

### 7.2.5 EARLY TERMINATION VISIT

If the participant chooses to terminate participation early, he or she will be contacted either in person or by phone to verify the decision to discontinue the study.

---

### 7.2.6 UNSCHEDULED VISIT

ACT intervention participants who are unable to attend a group session will be offered an individual session in order to review material with the group provider. This includes “make-up” sessions, which may occur due to planned or unplanned events (e.g., vacation or illness). “Make-up” sessions must occur (any time) prior to next scheduled session. These sessions will be scheduled based on the availability of both the participant and the provider. The make-up session may occur either in-person or remotely.

### 7.2.7 SCHEDULE OF EVENTS TABLE

	Screening	Baseline	8-week intervention period 								Follow-up Assessments 		Qualitative Interview
			Wk 1	Wk 2	Wk 3	Wk 4	Wk 5	Wk 6	Wk 7	Wk 8	Post 6-Wk 	Post 12-Wk 	
Consent		X											
Pre-Screen	X												
Eligibility		X											
Demographics	X	X											
Randomization 		X											
ACT session 1 			X										
ACT session 2 				X									
ACT session 3 					X								
ACT session 4 						X							
ACT session 5 							X						
ACT session 6 								X					
ACT session 7 									X				
ACT session 8 										X			
Likert Scale – Acceptability 			X	X	X	X	X	X	X	X			
SF-36		X 				X 					X 	X 	X 
PROMIS		X 				X 					X 	X 	X 
CPAQ		X 				X 					X 	X 	X 
CAAQ		X 				X 					X 	X 	X 
Qualitative Interview 													X

1. Determined by pre-screen chart review, screening phone call (with verbal consent), and confirmation of eligibility by research study personnel, after patient consents.
2. After consent and before completion of baseline measures.
3. ACT (intervention) participants only.
4. Within 2 weeks prior to intervention start date. These measures may be repeated in order to be within window.
5. +/- 7 day window
6. The qualitative interview may be conducted via phone or in person, any time from Week 9 through 12-Week follow-up; for ACT participants only.

7. Intervention and Follow up visits can be completed in person or remotely.

### 7.3 CONCOMITANT MEDICATIONS, TREATMENTS, AND PROCEDURES

All concomitant pain and psychiatric prescription medications taken during study participation will be recorded on the case report forms (CRFs). For this protocol, a prescription medication is defined as a medication that can be prescribed only by a properly authorized/licensed clinician. Medications reported in the CRF include concomitant pain and psychiatric prescription medications, over-the-counter pain medications, and non-prescription pain medications. In addition, information will be gathered about other treatments for pain, including acupuncture, massage, and physical therapy for each patient.

### 7.4 PROHIBITED TREATMENTS AND PROCEDURES

Treatment with other psychotherapies focused on pain management (i.e., cognitive behavioral therapy) will not be permitted for ACT intervention group members.

## 8 ASSESSMENT OF SAFETY

### 8.1 SPECIFICATION OF SAFETY PARAMETERS

All participants consenting to study participation will be provided with the contact information for the PI, [name], who is a licensed clinical psychologists and a provider at the Cancer Center. All participants will have access to psychosocial support services available at the Cancer Center.

#### 8.1.1 DEFINITION OF ADVERSE EVENTS (AE)

The following are considered to be adverse events:

- Increase in symptoms of depression and/or anxiety directly related to the act of participating in the intervention (i.e., scheduling appointments, additional visits).
- Increase in symptoms of depression and/or anxiety directly related to material presented in the intervention or the focus groups.
- Increases in anxiety and/or depression related to cancer diagnosis, treatment, impact of treatment on functioning and treatment side effects are **not** considered adverse events.

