## 2.3 POTENTIAL RISKS AND BENEFITS

### 2.3.1 KNOWN POTENTIAL RISKS

There are minimal risks to study participants. However, the ACT intervention, as well as measures included in assessment for all participants, will ask participants to reflect on both physical and psychological constructs that may be related to their cancer experience. This may result in distress. In the event that distress is acute, psychosocial support will be available for all participants. It is the expectation that participants in both groups will experience some benefit from active pain management intervention. All ACT groups will be directed by a licensed clinical psychologist in order to monitor for any distress in the group. Additionally, assessments of emotional functioning and pain experience (i.e., interference and severity) will be measured at the midpoint of the intervention in order to assess for any possible iatrogenic effect. These measures are precautionary in nature as there are no known potential risks for this intervention.

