## 8.3 TIME PERIOD AND FREQUENCY FOR EVENT ASSESSMENT AND FOLLOW-UP

The PI will record all reportable events with start dates occurring any time after informed consent is obtained until the completion of the 12-Week follow-up measures. At each study visit, the investigator will inquire about the occurrence of AE/ SAEs since the last visit. Events will be followed for outcome information until resolution or stabilization.

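### Adverse events are limited to mood symptoms attributed to the intervention, so AE counts cannot be compared between arms and worsening pain is not captured as an AE

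*Combined protocol and SAP*

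**What the plan says.** Section 8.1.1 of the protocol has two limbs that create an AE and one that removes it. The first is "Increase in symptoms of depression and/or anxiety directly related to the act of participating in the intervention". The second is "Increase in symptoms of depression and/or anxiety directly related to material presented in the intervention or the focus groups". The third states that "Increases in anxiety and/or depression related to cancer diagnosis, treatment, impact of treatment on functioning and treatment side effects are" not to be counted. Pain does not appear.

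Section 2.3.1 describes the risk more widely. It says that "the ACT intervention, as well as measures included in assessment for all participants, will ask participants to reflect" on matters tied to their cancer, and that this may be distressing. As a precaution, "assessments of emotional functioning and pain experience (i.e., interference and severity) will be measured at the midpoint of the intervention", with the stated aim of looking for an iatrogenic effect.

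On ascertainment, section 8.3 says: "At each study visit, the investigator will inquire about the occurrence of AE/ SAEs since the last visit". Section 7.2.3 says: "It is expected that all assessments will be delivered via REDCap Survey".

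On analysis, sections 10.3.3 and 10.3.10 compare SF-36 functioning and PROMIS pain between arms by repeated measures ANOVA over five time points. Section 10.3.1 makes inferential tests one-tailed at .05. Section 10 mentions neither AEs nor deterioration.

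**The concern.** Relatedness is normally a judgement made about an event after it has been recorded. Here it is a condition for the event to exist. That has three effects.

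- A participant who receives no ACT has nothing to which the event could be related.
- For a participant who does receive ACT, someone who knows the allocation decides whether worsening mood came from the sessions (an AE) or from the cancer and its treatment (not an AE).
- In a trial of chronic pain, worsening pain falls outside the definition, although section 2.3.1 names pain as something to watch for harm.

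The trial is meant to inform later research. If its AE listing is read by arm, the reader sees the effect of the definition and of unblinded attribution, and cannot separate either from an effect of ACT.

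**Working it through.** The plan states no AE rate, no harms test and no harms sample size, so there is no figure to reproduce. The check is mainly of the text, with one illustration.

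**Step 1: can a TAU-alone participant have an AE?** Sections 2.2, 4.2.1 and 4.2.2 use the word intervention for ACT. The first limb and the material part of the second therefore point to ACT. The second limb also mentions focus groups. The protocol describes none; section 7.2.4 describes one-on-one interviews, offered only to participants randomised to ACT. Distress caused by the questionnaires, which section 2.3.1 recognises in both arms, is not clearly covered by either limb. Mood worsening in a TAU participant that relates to the cancer is removed by the third limb.

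**Step 2: what decides an event in ACT?** Attribution decides it, and sections 4.1 and 10.5.1 state that there is no blinding.

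**Step 3: is pain covered?** It is not an AE in either arm. Section 8.1.2 (unanticipated problems) includes physical harm, but only if it was unforeseen and indicates that research procedures caused harm or that risk is higher than was known.

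**Step 4: what is compared by arm?** Sections 4.1 and 7.2.3 have all participants assessed at baseline, Week 4, Week 8 and the 6- and 12-week follow-ups. These are the five time points of the ANOVAs, so Week 4 emotional functioning and pain do enter the by-arm models. What is absent is a Week 4 contrast specified for harm and any count of individuals who got worse.

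**Step 5: illustration.** Let n be participants per arm, p the true proportion with worsening mood (assumed equal in both arms) and a the fraction of ACT cases attributed to the intervention.

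- Expected ACT count = n × p × a.
- Expected TAU count = 0 on the ordinary reading.

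Take n = 46 (section 5.3; also 92 / 2 from section 10.4), with 50 / 2 = 25 and 140 / 2 = 70 from the minimum and maximum enrolment. The values of p are assumptions. With a = 1:

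| n per arm | p = 5% | p = 10% | p = 20% |
|---|---|---|---|
| 25 | 1.25 vs 0 | 2.5 vs 0 | 5.0 vs 0 |
| 46 | 2.3 vs 0 | 4.6 vs 0 | 9.2 vs 0 |
| 70 | 3.5 vs 0 | 7.0 vs 0 | 14.0 vs 0 |

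With a = 0 every ACT entry is also 0. At p = 10%, for example, the apparent difference in proportions is p × a − 0, which runs from 0 to 10 percentage points according to attribution alone, while the true difference is 0.

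**The case against.** The strongest reply is that the AE listing is not the only harm information, and that several tempting conclusions go further than the documents allow.

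- **A reader might infer that the trial cannot compare harms at all, or that the midpoint check is never analysed by arm.** Neither is so. The two domains named in section 2.3.1 are measured in the same way in both arms and compared between arms, Week 4 included. What is missing is a comparison set up for harm.
- **A reader might infer that the one-tailed rule makes harm invisible.** That is too strong. The omnibus F-test of a repeated measures ANOVA has no direction, coefficients are to be reported with standard errors, and section 10.4 sizes the trial two-tailed. Still, section 10.3.1 sets one-tailed tests and the hypotheses in sections 2.2 and 4.2.2 favour ACT, so nothing in the plan directs the analyst to look for a difference against ACT.
- **A reader might infer that TAU is zero with certainty.** Section 6.1 lists TAU under a heading that refers to intervention groups, so another reading exists. It is the less natural one.
- **A reader might infer that worsening pain can never be reported.** Section 8.1.2 leaves a route, though a narrow one that again depends on attribution.
- **A reader might infer that ascertainment is unequal by design.** Section 8.3 requires the AE inquiry without restriction by arm. ACT adds eight weekly clinician-led sessions, while assessments are expected by online survey, so unequal detection is plausible. The documents do not state it.

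The reply also notes that this is a minimal-risk feasibility trial with no harms objective and no planned AE table by arm. That limits how serious the point is. It does not make the AE counts comparable.

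**Conclusion.** The point stands in limited form. As defined, AE counts depend on arm and on unblinded attribution, so they cannot be compared between arms, and worsening pain is not an AE. The by-arm comparison of mean SF-36 and PROMIS scores fills part of the gap. It does not show how many individuals deteriorated, and it contains no contrast specified for harm.

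The size can only be illustrated. The counts above rest on the ordinary reading of intervention as ACT, on assumed true rates of 5% to 20% that are equal in both arms, and, at their upper end, on every ACT case being attributed. They describe what someone tabulating AEs by arm would see; the plan itself specifies no such table. This is an inexpensive improvement to the harm data and not a flaw that undermines the feasibility aim.

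**What to change.** **Section 8.1.1.** Record any worsening of mood or pain in both arms regardless of cause, with relatedness to study procedures as a separate field. Ask both arms the same question at each scheduled assessment: Weeks 4 and 8 and the 6- and 12-week follow-ups. Correct the reference to focus groups so that it matches section 7.2.4.

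**Section 10.** Add a table by randomised arm of participants worse than baseline at Weeks 4 and 8 on SF-36 emotional well-being, PROMIS pain interference and PROMIS pain intensity. Give denominators, and mean differences with two-sided 95% confidence intervals. State in section 10.3.1 that the one-tailed rule does not apply to this table.

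**Cost.** One question added to the existing REDCap surveys, one field on the AE form and one table from data already collected. Treatment, visits and sample size do not change. The downside is more recorded events to classify, many of which will have nothing to do with the trial.
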